3.2 Study Rationale

In a mass balance trial, ¹⁴C-MSC2156119 was moderately metabolized in human subjects and a total of 10 different Phase 1 and Phase 2 metabolites were found. Total radioactivity was also mainly eliminated via feces (~78%) while only about 14% was recovered in urine. In feces, roughly 45% of the administered dose could be related to parent drug. This indicates a high extent of active secretion (likely via bile), but unabsorbed drug as well as reduction of N-oxides and hydrolysis of the glucuronide to parent drug may have also contributed to this high recovery. Based on AUC_{all} (which corresponds to the AUC_{0-240h} within the observation period), the M506 could be identified as major metabolite both with respect to European Medicines Agency (EMA) Guidance ICH M3(2) EMA/CPMP/ICH/286/1995 (4) and the draft Food and Drug Administration (FDA) Guidance for Industry – Drug Interaction Studies (5). Ratios of geometric mean values of AUC_{all}

of M506 to total radioactivity and to parent MSC2156119J compound were about 40.4% and 74.9%, respectively. M506 is formed from MSC2156119J with a median t_{max} of 24 hours ranging from 24 to 60 hours and showed an apparent geometric mean half-life of 93 hours ranging from 66 to 145 hours estimated on concentration data from 4 subjects. Urinary excretion was identified as minor route of excretion with an average recovery in urine of only 13.6% (range 8.8% to 17.7%).

According to the hepatic impairment guidances (FDA Guidance for Industry 2003 (9), EMA Guideline CPMP/EWP/2339/02 2005) it should be determined if alterations of excretory and metabolic activities by hepatic impairment can lead to drug accumulation.

Currently, enrolment of subjects into tepotinib HCC studies is restricted to subjects with mild hepatic impairment, ie, Child-Pugh class A.

This study will evaluate the PK and safety of tepotinib in subjects with mild (Child-Pugh class A) and moderate (Child-Pugh class B) hepatic impairment.

In most cases, HCC develops within an established background of chronic liver disease (70 to 90% of all patients) (10) and patients with cirrhosis have the highest risk of developing HCC (90 to 95% of subjects who develop HCC have underlying cirrhosis) (11). It is therefore assumed that the results of this study in subjects with hepatic impairment are also applicable to patients with HCC, especially patients with Child-Pugh class B.

In Part 1 of the study, PK and safety of a single dose of 500 mg tepotinib will be assessed in subjects with mild (Child-Pugh class A) and moderate (Child-Pugh class B) hepatic impairment in comparison to healthy subjects. A higher dose than 500 mg may be evaluated in Part 2 of the study in subjects with hepatic impairment if deemed necessary by the project team. In this case, the SMC will assess the results of Part 1 and make a recommendation on the tepotinib dose and which population (Child-Pugh class A or B) to be enrolled in Part 2. Healthy subjects will not be enrolled in Part 2 of the study.

This clinical study will be conducted in compliance with the clinical study protocol, ICH GCP, the Declaration of Helsinki, and any additional applicable regulatory requirements.

Based on the available nonclinical and clinical data to date, the conduct of the study specified in this protocol is considered justifiable.

4 Study Objectives

4.1 Primary Objective

• To assess the PK of tepotinib in subjects with various degrees of impaired hepatic function (in comparison to healthy subjects).

4.2 Secondary Objectives

- To further investigate the pharmacokinetics of tepotinib and its metabolites MSC2571109 and MSC2571107 in subjects with various degrees of impaired hepatic function (in comparison to healthy subjects)
- To assess safety and tolerability of tepotinib in subjects with various degrees of impaired hepatic function (in comparison to healthy subjects).

4.3 Other Objectives

Not applicable

5 Investigational Plan

5.1 Overall Study Design and Plan

This is a Phase 1, two-staged, open-label study to investigate the effect of various degrees of hepatic impairment on the PK, safety and tolerability of the c-Met kinase inhibitor, tepotinib.

Part 1 will include subjects with hepatic impairment (Child-Pugh class A [6 subjects] and Child-Pugh class B [6 subjects]) and a control group (6 healthy subjects matched 1:1 to 6 subjects with Child-Pugh class B with regard to age \pm 10 years, weight \pm 10 kg, and same gender). All subjects will receive a single dose of 500 mg tepotinib.

Part 2 of the study is optional and, if conducted, will evaluate doses above 500 mg up to 1000 mg in 6 subjects with hepatic impairment of either Child-Pugh class A or B.

An SMC may be established to evaluate the safety- and PK results of Part 1 if the overall development program of tepotinib decides to use higher doses than 500 mg (up to 1000 mg) in the Phase 2 or Phase 3 studies. The SMC will then make a recommendation on the tepotinib dose and which population (Child-Pugh class A or B) to be enrolled in Part 2 based on the safety- and PK results of Part 1. See Figure 1 for a diagram of the study design.

Subjects will be screened from Day -28 to Day -2. Subjects will be admitted to the study center on Day -1 and will remain inpatient at the study center under medical supervision until discharge on the morning of Day 4.

[figure not shown]
The treatment consists of a single-dose administration of 500 mg tepotinib on Day 1 in Part 1. The dose to be investigated in Part 2 will be determined by the SMC after evaluation of the safety- and PK results of Part 1.

Serial blood samples (PK and clinical laboratory assessments) and urine samples (clinical laboratory assessments) will be collected at the timepoints provided in Table 1. There is a PK sampling period of 2 weeks for healthy subjects and 3 weeks for hepatic impaired subjects.

The End of Study visit is planned on Day 15 for healthy subjects and on Day 22 for hepatic impaired subjects. An Early Termination visit will be conducted for subjects who withdraw

prematurely. The same assessments as for the End of Study visit will be conducted at the Early Termination visit.

Figure 1 Design Diagram

Part 2 of the study is optional.

CSR = Clinical study report; HCC = Hepatocellular carcinoma; PK = Pharmacokinetic, SMC = Safety Monitoring Committee.

5.2 Discussion of Study Design

A parallel design with a small number of hepatic impaired subjects and controls with normal hepatic function is the standard design for hepatic impairment studies, in line with the FDA and EMA guidances/guidelines. According to the hepatic impairment guidances (FDA Guidance for Industry 2003, EMA Guideline CPMP/EWP/2339/02 2005), 6 evaluable subjects should be enrolled per group. The control group will consist of 6 healthy subjects with normal hepatic function, matched 1:1 to the subjects with moderate (Child-Pugh class B) impaired hepatic function with regard to age \pm 10 years, weight \pm 10 kg, and same gender.

Subjects with hepatic impairment will be assigned to a group of mild (Child-Pugh class A) or moderate (Child-Pugh class B) hepatic impairment at Screening by use of the Child-Pugh system. See Table 2 and Table 3.

Table 2 Child-Pugh Grades/Class of Hepatic Impairment

Child-Pugh Score	Child-Pugh Grade/Class	Severity of Hepatic Impairment
5-6	А	Mild
7-9	В	Moderate
10-15	С	Severe ^a

a Subjects with severe hepatic impairment will not be included in this study

Grading of hepatic impairment by use of the Child-Pugh system, including ultrasound examination for detection and classification of ascites as well as assessment of hepatic encephalopathy, will only be performed in subjects with hepatic impairment.

Table 3 Child-Pugh Criteria

	Points Scored for Observed Findings (14, 15, 16)								
	1	2	3						
Encephalopathy grade ^a	none	1 or 2 or medically controlled c	3 or 4 or medically controlled ^c						
Ascites ^b	absent	slight or medically controlled ^c	Moderate or medically controlled ^c						
Serum bilirubin (mg/dL)	< 2	2 to 3	> 3						
Serum albumin (g/dL)	> 3.5	2.8 to 3.5	< 2.8						
International Normalized Ratio (INR)	< 1.70	1.70 to 2.20	> 2.20						

- a Encephalopathy will be assessed by an experienced physician at Screening using the following criteria:
 - Grade 0: normal consciousness, personality, neurological examination, electroencephalogram
 - Grade 1: restless, sleep disturbed, irritable/agitated, tremor, impaired handwriting, 5 cycles per second waves
 - Grade 2: lethargic, time-disoriented, inappropriate, asterixis, ataxia, slow triphasic waves
 - Grade 3: somnolent, stuporous, place-disoriented, hyperactive reflexes, rigidity, slower waves
 - Grade 4: unrousable coma, no personality/behavior, decerebrate, slow 2 to 3 cycles per second delta activity.
- Ascites will be assessed by an experienced physician by physical examination as well as ultrasound examination at Screening using the following criteria:
 - Absent: No ascites is detectable by manual and also not by ultrasound investigation.
 - Slight: Ascites palpitation doubtful, but ascites measurable by ultrasound investigation.
 - Moderate: Ascites detectable by palpitation and by ultrasound investigation.
- c Diagnosis and treatment of medically controlled subjects must be confirmed by the subject's medical records.

The majority of healthy volunteers are not expected to have measurable concentrations after Day 15; therefore sampling until Day 15 is sufficient. Sampling for one additional week for the subjects with hepatic impairment to cover a possibly longer half-life appears appropriate. This was confirmed with a compound model developed in Simcyp, which allowed to simulate the impact of change in active liver size in subjects with hepatic impairment. Simulations using the population representatives indicate that the concentration reached after 21 days decline is attained in subjects with hepatic impairment about 1 to 2 days later, ie, the predicted difference between the healthy and subjects with moderate hepatic impairment.

Model limitations include non-consideration of possibly reduced metabolic enzyme expression. Of the number of physiological changes known to occur in subjects with hepatic impairment (size of active liver, plasma protein binding, blood flow, metabolizing enzymes), only the reduction of active hepatocytes could be implemented in the model. Thus the effect of hepatic impairment could be stronger than predicted.

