5.3.2 Exclusion Criteria

All subjects:

- 1. Subject has taken an investigative medication within 30 days prior to administration of IMP
- 2. Subject has donated blood within 60 days or plasma within 14 days prior to Screening
- 3. Subject is lactating
- 4. Diseases or surgeries of the gastrointestinal tract, which could influence the gastrointestinal absorption or motility
- 5. A history of epilepsy
- 6. A history of malignant diseases other than basalioma
- 7. Clinically relevant allergies that require medical treatment, as judged by the Investigator
- 8. Inability to refrain from alcohol intake during confinement. Subjects should not consume more than 14 (women) or 21 (men) units of alcohol a week (unit = 1 glass of wine (125 mL) = 1 measure of spirits = ½ pint of beer)
- 9. Any other clinically relevant disease, which in the Investigator's opinion would exclude the subject from the study
- 10. Inability to communicate or cooperate with the Investigator (eg, language problem, illiterate, poor mental status) or to comply with the requirements of the entire study, including dietary restrictions
- 11. Smoking > 10 cigarettes per day, or equivalent use of other forms of nicotine (ie, patches, gum, chewing tobacco, vaping) for the duration of the study
- 12. Antacid drugs, H2-blocker and proton pump inhibitors might affect the absorption of tepotinib. H2-blocker or proton pump inhibitors should be stopped 5 days prior to Day 1 until Day 2. Antacids should not be taken 1 hour before the IMP administration until 2 hours after the IMP administration.
- 13. Renal dysfunction (defined as creatinine clearance < 60 mL/minute, calculated by use of the Cockcroft-Gault formula)

Healthy Subjects:

- 14. Presence of hepatitis B or hepatitis C or previous infection with hepatitis C, treated with Sofosbuvir or other antiviral compounds
- 15. Use of any medication, including multivitamin preparations, received within 10 days prior Day 1 or 6 times the elimination half-life, whichever is the longest, until the End of Study visit,

except the occasional use of paracetamol/acetaminophen or ibuprofen (not > 500 mg per day) within 7 days before Day 1 until the End of Study visit.

Subjects with impaired hepatic function:

- 16. Primary biliary liver cirrhosis
- 17. Nonstabilized chronic heart failure (New York Heart Association Class III and IV)
- 18. Hepatocarcinoma
- 19. Hepatic encephalopathy Grade III and IV

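### Table 3 gives medically controlled encephalopathy and ascites both 2 and 3 points, so the Child-Pugh class of some boundary subjects is not fixed

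*Protocol*

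**What the plan says.** Section 5.2 assigns subjects with hepatic impairment to the mild or moderate group at Screening, using Tables 2 and 3. Table 2 sets class A at 5 to 6 points, B at 7 to 9 and C at 10 to 15. Its footnote adds: "Subjects with severe hepatic impairment will not be included in this study".

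Table 3 scores five items at 1 to 3 points each, under the header "Points Scored for Observed Findings". Two rows mention medical control:

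| Item | 2 points | 3 points |
|---|---|---|
| Encephalopathy grade | "1 or 2 or medically controlled" | "3 or 4 or medically controlled" |
| Ascites | "slight or medically controlled" | "Moderate or medically controlled" |

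All four cells carry footnote c, which begins "Diagnosis and treatment of medically controlled subjects must be confirmed" and names the subject's medical records as the source. It says nothing about points. Footnotes a and b define the observed grades and place both assessments at Screening. Section 7.2.2 repeats the allocation and refers back to Tables 2 and 3. Exclusion Criterion 19 (Section 5.3.2) reads "Hepatic encephalopathy Grade III and IV", with no time qualifier.

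**The concern.** The same description, medically controlled, leads to two different scores, and no sentence says how to choose. Two assessors, or the two study centers, could score the same subject differently and both comply with the protocol.

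Child-Pugh class is the exposure variable of the study, so a one-point difference at a boundary has several consequences:

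- At A/B, it decides which of the two groups of 6 the subject joins. One subject is one sixth of a group.
- Because the healthy controls are matched 1:1 to class B subjects on age, weight and gender (Section 5.1), it also decides whom a control must match.
- It sets the level of the hepatic function group, the only fixed effect in the primary ANOVA (Section 8.5.2).
- At B/C, it decides whether the subject may be enrolled.

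Classification happens at Screening under the protocol, so an analysis plan cannot settle it afterwards.

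**Working it through.** **Inputs.** Item scores come from Table 3 and class bands from Table 2. A controlled sign is scored 2 on the low reading and 3 on the high reading.

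**Table 2 range.** Five items at 1 to 3 points give 5 × 1 = 5 up to 5 × 3 = 15, which matches the printed range. The defect therefore lies in the Table 3 cells and not in the bands.

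**One controlled sign.** Let S be the sum of the other four items. The total is S + 2 or S + 3.

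| S | Low total | High total | Class |
|---|---|---|---|
| 4 | 6 | 7 | A or B |
| 5 | 7 | 8 | B |
| 6 | 8 | 9 | B |
| 7 | 9 | 10 | B or C |
| 8 or more | 10 or more | 11 or more | C |

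S = 4 occurs only when all four other items are at 1 point.

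**Both signs controlled.** Let L be the sum of bilirubin, albumin and INR points. The total runs from L + 4 to L + 6.

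| L | Possible totals | Class |
|---|---|---|
| 3 | 7 to 9 | B |
| 4 | 8 to 10 | B or C |
| 5 | 9 to 11 | B or C |
| 6 or more | 10 or more | C |

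**Listing the cases.** Take encephalopathy as 1, 2 or controlled (observed Grade III and IV is excluded), ascites as 1, 2, 3 or controlled, and each laboratory item as 1, 2 or 3. Require at least one controlled sign and class A or B on the low reading.

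- One sign: 2 patterns at 6/7 (A to B), 8 at 7/8 and 19 at 8/9 (stay B), 29 at 9/10 (B to C).
- Two signs, both low against both high: 1 at 7/9 (stays B), 3 at 8/10 and 6 at 9/11 (B to C).
- Total: 2 + 8 + 19 + 29 + 1 + 3 + 6 = 68, of which 2 move A to B, 29 + 3 + 6 = 38 move B to C, and 8 + 19 + 1 = 28 stay B.

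These counts locate the boundaries. They are not frequencies, because the patterns are not equally likely. Only the 2 A/B patterns can mix mild with moderate subjects.

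**Ascites row alone.** Suppose controlled encephalopathy is left out and only ascites is controlled, with encephalopathy at 1 or 2 points. The number of patterns is 1 for S = 4, 3 + 1 = 4 for S = 5, 6 + 3 = 9 for S = 6 and 7 + 6 = 13 for S = 7. That leaves 1 pattern A to B and 13 B to C, so the problem does not depend on the encephalopathy row.

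**A further opening.** A controlled subject with no detectable ascites, or no current encephalopathy, also fits the 1-point cell. If that were allowed, S = 5 would give 6, 7 or 8, a second A/B split. The counts above do not include it.

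**The case against.** The strongest reply is that the table has a coherent reading. Each mention of medical control is attached to a severity, so a controlled sign would take the points of its severity before treatment. Every cell then has its own meaning, the repetition has a purpose, and footnote c sends the assessor to the records where earlier severity would be found. Medical control is in any case a treatment status that examination alone cannot establish, which weakens an argument from the column header. Exclusion Criteria 20, 21 and 29 state look-back windows and Criterion 19 does not, so Criterion 19 plausibly means current status. The 3-point encephalopathy cell would then serve subjects formerly at Grade 3 or 4 and now controlled.

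This is a fair inference, but no sentence states it. The header speaks of observed findings, the assessments are placed at Screening, and footnote c asks for diagnosis and treatment, not for the earlier grade or extent that this reading would need. If Criterion 19 instead covers history, such subjects are excluded and the encephalopathy part of the problem shrinks, but the ascites row is unchanged.

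The reply is right that the A/B effect is confined to one situation, that B/C cases concern enrollment and not mixing of groups, and that no effect on the primary estimate has been shown. Grading by an experienced physician does not supply the missing rule. The ALBI and ODWG evaluation in Section 8.5.3 is unaffected by the problem, but it does not replace Child-Pugh class for eligibility, matching or the primary model.

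**Conclusion.** The concern holds. As printed, a medically controlled sign can score 2 or 3, and for subjects at a boundary the protocol does not determine the class. The affected cases are:

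- one controlled sign with the other four items at 1 point (6 or 7, A or B);
- one controlled sign with the other four summing to 7 (9 or 10, B or C);
- two controlled signs with the laboratory items summing to 4 or 5 (8 to 10 or 9 to 11, B or C).

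Subjects with no controlled sign, controlled subjects away from a boundary, and the healthy controls' own status (they are not graded) are unaffected. The conclusion assumes only that the repeated wording is the sponsor's own. The same pattern in both rows, with the same footnote, supports that. The number of subjects involved is unknown because the protocol gives no frequency of medical control. The point should be fixed because class drives eligibility, grouping, matching and the primary factor in groups of only 6.

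**What to change.** Reconcile the two encephalopathy cells, the two ascites cells, footnote c and Exclusion Criterion 19 so that each combination of findings and treatment gives exactly one score. The wording should also settle whether the 1-point cells can apply to a controlled subject, and whether Criterion 19 refers to current status or to history. Which score applies is for the sponsor to decide. Apply the one rule at both study centers, and re-check the scores of any medically controlled subject already screened before group assignment and control matching are final.

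The cost is a text correction to Table 3, its footnote and Criterion 19, plus a review of the screening worksheets for medically controlled subjects. It needs no additional subjects or procedures, and the sample size is unchanged.

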5.2.1 Scientific Rationale for Study Design

The study design includes matched pairs of patients with hepatic impairment and healthy volunteers and is the recommended design to characterize the effects of impaired hepatic function on the PK of a drug. Part 2 is required if within the total tepotinib program, a higher therapeutic dose than 500 mg once daily will be used.

5.2.2 Justification for Dose

In clinical studies in healthy subjects, good safety and tolerability was observed after administration of single doses of 30 mg to 500 mg.

From patients with solid tumors, safety data is available for a dose regimen of 1400 mg tepotinib once daily. Even in case of a significant delay in elimination in patients with hepatic impairment, exposure in this study with single dose administration is expected to be less.

For Part 1 of this study, the recommended Phase 2 dose of 500 mg has been selected.

Tepotinib will be administered in the fed state, which is also the recommended mode of administration in clinical studies with tepotinib performed thus far.

Part 2 of the study is optional and will be conducted if the overall development program of tepotinib decides to use higher doses than the 500 mg in Phase 2 and Phase 3 studies. An SMC will make a recommendation on the tepotinib dose and which population to be enrolled in Part 2. Further details are provided in Section 5.1.

5.2.3 Rationale for Endpoints

The primary and secondary endpoints are relevant exposure parameters that are required to assess the impact of hepatic impairment on the exposure of tepotinib.

The rationale for including metabolites as secondary endpoints are as follows:

M506 was identified as the only major circulating metabolite and contributes with a low extent to the overall activity. Its contribution to safety and tolerability is not evaluated by nonclinical safety, as tepotinib is developed under the ICH S9 guidance.

M506 is formed from MSC2156119J with a median t_{max} of 24 hours, ranging from 24 to 60 hours, and showed an apparent geometric mean half-life of 93 hours, ranging from 66 to 145 hours, estimated on concentration data from 4 subjects. M506 consists of 2 enantiomers, the S-enantiomer, MSC2571107, and the R-enantiomer, MSC2571109, which have been included as secondary endpoints. MSC2571109 represents the major human plasma metabolite of tepotinib (64.6% of parent AUC_{0-240h}), while MSC2571107 is a metabolite of less significance (4.54% of parent AUC_{0-240h}). A bioanalytical assay is available, which analyzes tepotinib and the enantiomers.

5.2.4 Risks

On the basis of available clinical data, asymptomatic increase of lipase and amylase are considered as an identified risk of tepotinib. Such elevations have been reported for a number of other tyrosine kinase inhibitors with molecular targets other than c-Met (eg, sunitinib, imatinib, sorafenib) and can therefore be regarded as a class effect. The underlying mechanism that causes the enzyme elevation is unknown. The pancreas was not identified as a potential target organ in animal toxicology studies. No pancreatitis has been reported so far.

Tepotinib was identified as a P-glycoprotein (P-gp) substrate, as well as an inhibitor of P-gp, BCRP, OCT1, OCT2, MATE1, and MATE2. Intestinal and systemic drug-drug interactions on the transporter level with relevance cannot be ruled out. In vitro drug transporter interaction studies revealed a pronounced inhibition of OCT1, OCT2, and MATE2 by the major metabolite MSC257119A with the potential for clinically relevant drug-drug interactions considering its current mean exposure at steady state in clinical studies.

